We plan to enroll 150 patients with the goal of 112 completing the study (25% drop-out rate). We will plan to consent up to 250 patients taking into account screening failures or hospital readmissions that occur prior to the first outcome visit. Enrollment in the study will be defined as participation in the first outcome measurement session at baseline once discharged home. The goal of the study is to obtain a representative sample of older adults with multiple comorbid conditions who receive home health physical therapy. Both sexes and all races are included in the study, however the Veteran population is predominantly male and Caucasian, which will be reflected in the enrollment. We will also consent up to 150 Caregivers, for a total of up to 400 consented.

Study Design and Research Methods:

PHIT Rationale

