D2.3. Subject identification, recruitment, and randomization: Participants will be recruited from the Denver VAMC, UCHealth Highlands Ranch, and UCHealth Broomfield. Two hundred and fifty Veterans will be recruited (3-4 patients per month) with at least 112 expected to complete through the 60 day episode of care to accommodate for the potential re-hospitalization rate of 20-30% among home care recipients³² and drop-outs for other reasons. We had no difficulty recruiting patients for our preliminary study (3-4 patients/month). The Denver VAMC coordinates home health services for approximately 300 Veterans/month. Of these, approximately 30/month would be eligible for this study (> 55 years old; receiving home health PT services for decreased mobility after an acute hospitalization; living within the Denver metropolitan area). Therefore, recruitment of 3-4 patients/month through the Denver VAMC alone should allow us to meet our recruitment goals

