The characteristics of the time trajectory (30, 60, 90 and 180 days of follow-up) for treatment effects will also be analyzed in secondary analyses to elucidate the mechanism and inform the

development of methods to improve long-term outcomes. The analytic methods will include maximum likelihood estimates from a repeated measures model of the mean effect at each of the measurement times.⁸⁵ The trend in means will be evaluated using a linear contrast as the summary measure of greatest interest.⁸⁶ This approach will evaluate whether there are differences in the first-order trends (slope) between intervention groups. Finally, we will estimate adverse events rates (falls, emergency department visits, nursing home days, or rehospitalizations) for each arm and compare rates between arms using a likelihood ratio test. We will additionally investigate whether training volume significantly explained additional variability in functional gains within the PHIT group using regression analysis.

Sample Size Estimates

Statistical power was estimated based on the results of a pilot study of 18 participants: 8 were randomized to PHIT, 10 to the UC interventions (results for SPPB, gait speed, and mPPT are shown in Figure 2). We observed a between group difference \pm SD in gait speed of 0.18 \pm 0.29 meters/second (m/s) in the preliminary study. Thus, a sample size of 112 patients completing the study (56/group) will provide 90% power (assuming the same pooled SD in both groups to be conservative) to detect differences at least that great. This represents 1.8 times a clinically important difference of 0.1m/s.⁴⁶ This estimate is conditional upon using a 2-sided, alpha = 0.05 level 2-group t-test.

We expect that we will consent 250 Veterans and spouses for the study, with allowance for a 25% screening failure. Screening failures that occur after consent is obtained and before enrollment in the study may include a change in medical status during hospitalization requiring a discharge to a location other than home health (e.g skilled nursing facility), a hospital re-admission which occurs after hospital discharge but prior to the baseline assessment being completed, or a failure to meet specific performance inclusion criteria (e.g. a Veteran or spouse who lacks the ability to ambulate 10 feet without at least minimal physical assistance [more than supervision or light touching for steadiness] from another person)

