Enrollment in the study will be defined as participating in the baseline functional performance measures. We expect to enroll 150 Veterans and spouses into the study, with 112 needed to complete to meet study goals. From our experiences and available data, we anticipate a 25% drop out. Caregivers will be consented after a Veteran or spouse is enrolled in the study, thus we anticipate enrolling 150 caregivers. Caregivers will undergo assessment of caregiver burden on the outcome measurement schedule above until the conclusion of the 180 day study period, or until the Veteran or spouse for whom they give care is lost to the study (e.g re-hospitalized)— similarly, we anticipate to need 112 to complete.

Thus, in total, we anticipate consenting 250 Veterans and spouses for the study, enrolling 150 of them, and expecting 112 to complete. We will additionally be consenting 150 caregivers with 112 expecting to complete. For the total study, we will be consenting 400 participants (250 Veterans and spouses, 150 caregivers) and expecting 224 to complete (112 Veterans and spouses, 112 Caregivers). These numbers have been provided to as part of the grant application process to the Veterans Administration Rehabilitation Research and Development Service and were favorably reviewed and pending a funding announcement for a Merit Award (R01 equivalent).

G. Summarize Knowledge to be Gained:

There is a growing recognition that acute hospitalization contributes to long-term disability for hospitalized older adults—who are 60 times more likely to develop disability than those who are not hospitalized. Older Veterans are particularly vulnerable to functional decline after

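### The 25% drop-out allowance equals the midpoint of the plan's own re-hospitalisation range, so reaching 112 completers depends largely on whether readmitted participants are still measured at day 60

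*Combined protocol and SAP*

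**What the plan says.** Three places give the completer target.

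- Section IV.B (Description of Population to be Enrolled): "We plan to enroll 150 patients with the goal of 112 completing the study (25% drop-out rate". Enrolment means taking part in the baseline session at home.
- Sample Size Estimates repeats 150 enrolled and 112 completing: "we anticipate a 25% drop out". It also says that "a sample size of 112 patients completing the study (56/group) will provide 90% power", for a difference of 0.18 m/s and an SD of 0.29 m/s, using a "2-sided, alpha = 0.05 level 2-group t-test".
- Section D2.3 starts from 250 recruited, with "at least 112 expected to complete through the 60 day episode of care". It gives the reason: "to accommodate for the potential re-hospitalization rate of 20-30% among home care recipients" "and drop-outs for other reasons". No rate is given for the other drop-outs.

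The plan is not uniform on what follows a readmission after enrolment. Sample Size Estimates, on when caregiver assessments end, refers to the point at which the participant "is lost to the study (e.g re-hospitalized". The stopping criteria in Section C withdraw an admitted participant only if the study physician also finds that person unsafe or unsuitable for high-intensity rehabilitation. Missing Data (Section D) keeps non-compliant participants in follow-up but does not mention readmission.

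**The concern.** D2.3 names two sources of loss, and one of them alone is put at 20-30%. The allowance meant to cover both is 25%. At the middle of the range, if readmission means loss, nothing is left for other causes. At the top, re-hospitalisation alone exceeds the allowance. A statement that at least 112 will complete needs more support than that.

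Two things are at stake. The first is the number of day-60 gait speeds available for the primary analysis, and hence its power. The second is who would be missing. Missing Data limits the intent-to-treat analysis to patients with outcome measurements and plans prevention in place of statistical adjustment. The Data Analysis Plan compares re-hospitalisation rates between arms, so readmission is itself an outcome that may differ by treatment. In the two small pilots (10 and 18 participants; D1.3 and D1.4), no re-hospitalisation was reported under PHIT. Usual care had 3 in the first pilot and, in the second, 6 episodes in 2 people, not split between emergency visits and admissions. These numbers are too small to establish a difference, but they show how ending measurement at readmission could make missing data depend on arm.

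**Working it through.** **Inputs.** Difference 0.18 m/s, SD 0.29 m/s, two-sided alpha 0.05, two-group t-test, 56 per group (Sample Size Estimates). 150 enrolled and 25% drop-out (Section IV.B and Sample Size Estimates). Re-hospitalisation *r* = 20-30% (D2.3). Other drop-out *o*: not given, so 0% is shown first, then 5% and 10% as assumptions.

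**The plan's own figures.** With *n* per group, the noncentrality is 0.18 / (0.29 × √(2/n)) on 2n − 2 degrees of freedom. At n = 56 it is 0.18 / (0.29 × 0.1890) = 3.28, and the power is 0.902. The smallest n giving at least 90% is 56 per group, or 112 in total. Enrolment: 112 / (1 − 0.25) = 149.3, rounded up to 150; conversely 150 × 0.75 = 112.5. Both steps reproduce.

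**Room inside the allowance.** Going from 150 to 112 permits a loss of 1 − 112/150 = 25.3%. If every re-hospitalisation is a loss, the room left for other causes is:

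- r = 20%: 25.3 − 20 = 5.3 points
- r = 25%: 25.3 − 25 = 0.3 points
- r = 30%: 25.3 − 30 = −4.7 points

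**Completers and power if every re-hospitalisation is a loss.** Completers = 150 × (1 − r − o); power from the noncentral t with half the completers in each group.

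| r | o = 0 | o = 5% (assumed) | o = 10% (assumed) |
|---|---|---|---|
| 20% | 120; 0.92 | 112.5; 0.90 | 105; 0.88 |
| 25% | 112.5; 0.90 | 105; 0.88 | 97.5; 0.86 |
| 30% | 105; 0.88 | 97.5; 0.86 | 90; 0.83 |

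Only the first column uses rates found in the documents.

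**If readmitted participants are partly retained.** Suppose half of them lack a day-60 gait speed (an assumption). The loss from re-hospitalisation is then 10-15%, which leaves 25.3 − 10 = 15.3 to 25.3 − 15 = 10.3 points for other causes. On that basis 112 is within reach across the whole range.

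**The case against.** The strongest reply is that the plan does not generally treat readmission as loss. The rule written for participants is the conditional one in Section C. The adverse-event script asks about hospitalisations since the last visit, and re-hospitalisation rates are to be compared between arms. Both suggest that many readmitted participants are expected to stay. The contrary phrase is a parenthesis about caregivers. This largely stands: 112 may well be reachable. But D2.3 still gives re-hospitalisation as a reason for the margin, and no section states what share of readmitted participants will lack a day-60 measurement.

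A second reply is that the D2.3 sentence starts from 250, so it covers attrition of 1 − 112/250 = 55%. That is a fair reading of the sentence. However, Section IV.B assigns screening failures and readmissions before the first outcome visit to the step from 250 to 150, and baseline falls within 48 hours of returning home (D2.1). Some re-hospitalisation belongs to that short window, but the plan gives no split, and after it only the 25% remains.

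A reader might go further and infer that 112 completers and 90% power cannot follow from the plan's figures, or that power falls to 0.83. The documents do not support either. At 20% re-hospitalisation plus 5% other loss, 112 does follow. The 0.83 needs the top of the range, the loss of every readmitted participant and an assumed further 10%, all together.

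Nor do the two descriptions of the 112, one through day 60 and one on completing the study, contradict each other. They simply leave open which time point the number refers to.

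Finally, the primary model adjusts for baseline gait speed, which may recover some power. The stated power takes no credit for this, and the plan gives no correlation from which to size it.

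**Conclusion.** The point holds as a gap in the justification of the completer number, of modest size. The power calculation for 112 completers is correct. What is unsupported is that at least 112 will be reached. If readmitted participants are lost, the documents' own rates give 105 to 120 completers and power of 0.88 to 0.92 before any other drop-out, and 112 holds only towards the low end of the range. If many of them are still measured, 112 is reachable. The conclusion rests on applying the 20-30% to the 150 enrolled, which D2.3 does not state explicitly. The loss of power is small, about two points at worst on the documents' rates. The possibility that missing data depend on arm is an equally good reason to settle the matter.

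**What to change.** 1. Reconcile D2.3, the stopping criteria in Section C and Sample Size Estimates on what happens to a participant after a readmission. The clinical withdrawal rule is for the investigators to settle; the sections need only agree.
2. State that re-hospitalisation alone does not end outcome follow-up: day-60 gait speed is sought for every enrolled participant who has not withdrawn or been withdrawn, and only those without that measurement count toward the 25%.
3. Tie the 112 to the day-60 primary endpoint wherever it appears.
4. If readmitted participants are in fact to be counted as lost, restate the expected completers as about 105-120 and the power as 0.88-0.92, before other drop-outs.

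The cost is a few additional follow-up visits within the existing schedule, or a slightly less favourable stated power. No added enrolment is needed.

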[name] (Co-Investigator), [name] (Co-Investigator), [name] (Co-Investigator), and [name] Ha (Co-Investigator) will identify patients at the Rocky Mountain Regional VAMC, [name] [name] (Co-Investigator) will identify patients at UCHealth Highlands Ranch, and [name] will identify patients at UCHealth Broomfield who meet the inclusion criteria daily (Figure 3) as part of the direct treatment relationship and face to face contact with potential subjects. A PRA under the supervision of Drs. [name], [name], [name], Ha, [name], and [name] will also screen medical records daily for potential research subjects who meet study criteria, and review verbally or by phone with the study physicians before approaching patients. The PRA will ask eligible (as identified by the study CO-I physicians) and willing patients to sign a consent form during the hospital stay. If patients are identified in the hospital as eligible in a face-to-face encounter, but are discharged before they are consented, then a research assistant or research physical therapist will ask eligible and willing patients to sign the consent form in the home setting. Additionally, clinicians within the Denver metro area will be informed of the study and will be provided with study flyers and with HIPAA A forms that they will give to their patients who meet eligibility criteria and who are interested in the study. If the potential participant is interested in learning more about the study, but chooses not to sign the HIPAA A form, they will be provided with a flyer. If the potential participant is interested in learning more about the study and chooses to sign the HIPAA A form, they will be contacted by phone by a study team member and will be asked screening questions from the phone screen script. If potential participants meet all study inclusion criteria and want to participate, a study team member will go to the potential participant's home and will conduct the informed consent process prior to baseline testing. In either case, documentation will be made in the Veteran's medical record (CPRS) indicating they have enrolled in a research study according to VA protocols for clinical research.

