After patients are consented, they will be randomized to either the PHIT treatment group or UC group using a randomization table that will be prepared by [name] (biostatistician) and held by the home health discharge coordinator at the VA who coordinates all referrals to the home health agency. Randomization assignments will be computer generated using random block sizes of 4 and 6. Randomization will occur via a centralized computer randomization system.

The discharge coordinator will then refer the patient to the home health agency who is delivering the intervention (The Visiting Nurses Association or Berkley Home Health) and inform the agency of the group assignment and ensure that the appropriately trained therapist (UC or PHIT) is scheduled to see the patient. The PRA will then provide the patient contact information to a blinded outcomes assessor (physical therapist or trained research assistant) to complete the baseline evaluation (functional tests and questionnaires). Therapists will be told not to reveal or discuss their assigned protocol to other therapists. [name] has successfully worked with the VNA to train PT staff and implement the proposed investigation for the preliminary data. This protocol has been followed for 22 patients recruited to-date without difficulty, and was successfully implemented, assessed, and the pilot data published.

Caregivers will be approached and, if eligible and willing, consented in the home setting of an enrolled Veteran. A research assistant will explain the study and the goals, and ask eligible caregivers to participate in filling out the caregiver burden inventory after signing a HIPAA waiver. We will only collect and record age (categories by decade) and gender of the caregiver in addition to caregiver burden scores.

D2.4. Interdisciplinary Coordination of Care: Following enrollment, Drs. [name], [name], [name], [name], [name], and Ha will remain involved in the interdisciplinary coordination of patient care as the physician contact following hospital discharge.

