Other home health services: In addition to physical therapy home health services, we recognize individuals may receive additional home services (e.g. nursing, occupational or speech therapy). We expect that the frequency of these additional services will not be different between groups because of randomization, but we will carefully track and report the total

numbers of these additional services.

D2.6. Treatment Fidelity across PHIT therapists

Treatment fidelity is critical to the success of the proposed intervention because of the use of multiple physical therapists. [name] has extensive experience with treatment fidelity for clinical trials involving rehabilitation of a multitude of patient populations. From these experiences, we have established mechanisms to assure the consistency of treatments across therapists. The availability of three PHIT-trained therapists and 3 UC therapists, covering different geographical areas in Denver through the Denver Visiting Nurses Association and Berkley Home Health will allow us to enroll all eligible patients, regardless of location. [name], and the research physical therapists ([name], PT and [name], PT) will provide 2-3 initial training sessions to therapists providing UC and PHIT interventions to review treatment protocols and documentation.

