A manual will be provided to each clinician with protocol details, clinic and home exercise pictures, documentation forms, and study contact information. Research Physical Therapists will review the intervention data sheets biweekly, and will conduct monthly phone meetings with the PHIT and UC physical therapists. If the treatment fidelity is below 90%, additional training sessions will be scheduled with individual therapists. Treatment fidelity data will provide information on the adherence of the PT to the interventions, the adherence of the participants to the prescribed activities, and will provide an opportunity to address potential study problems (see Appendix). In addition, every month for the first year, and every three months thereafter, treating therapists will meet to discuss treatment guidelines and any issues that have surfaced. For each agency therapist, the research physical therapists will observe 4-5 home sessions for the first 2 patients. These on-site observations may be supplemented with video conferencing during treatment sessions for additional oversight as necessary. Should new therapists require training during the course of the investigation, the same procedures for initial training and monitoring will be implemented. Each treating therapist will fax documentation weekly to ensure protocols are being followed.

Blinding of Research Staff: Only the research physical therapists conducting staff training, and the VNA HH or Berkley Home Health agency manager will have full knowledge of group assignment. Outcome data will be assessed by Physical Therapist Outcomes Assessors who will remain blinded to treatment group. Intervention PTs will only provide either PHIT or UC intervention. Patients will be instructed not to discuss what they do during their home physical therapy sessions with the Physical Therapist Outcomes Assessor to maintain blinding, and also be asked to not share the group assignments during any care coordination meetings.

C. Description, Risks and Justification of Procedures and Data Collection Tools:

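### Research physical therapists who know past allocations may take home consent before randomisation in blocks of 4 or 6: a small, cheaply closed opportunity for selection bias

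*Combined protocol and SAP*

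**What the plan says.** Section D2.3 describes three routes to consent.

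- **In hospital:** the PRA asks patients whom the co-investigator physicians have judged eligible.
- **Identified in hospital but discharged first:** "then a research assistant or research physical therapist will ask eligible and willing patients to sign the consent form in the home setting".
- **Referred by community clinicians:** a member of the study team, with no role given, telephones and screens the patient. A member of the team then takes consent at home.

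The same section places allocation after consent: "After patients are consented, they will be randomized to either the PHIT treatment group or UC group using a randomization table". The table is "held by the home health discharge coordinator at the VA who coordinates all referrals to the home health agency", and assignment runs through a central computer system. On the sequence itself: "Randomization assignments will be computer generated using random block sizes of 4 and 6". Stratification is not mentioned.

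Section D2.6 sets out what else the research physical therapists do. They are among those who "will provide 2-3 initial training sessions to therapists providing UC and PHIT interventions". It continues: "Research Physical Therapists will review the intervention data sheets biweekly, and will conduct monthly phone meetings with the PHIT and UC physical therapists". It adds: "Each treating therapist will fax documentation weekly to ensure protocols are being followed". They also observe home sessions. The paragraph on blinding of research staff states: "Only the research physical therapists conducting staff training, and the VNA HH or Berkley Home Health agency manager will have full knowledge of group assignment". That paragraph protects outcome assessment and is silent on recruitment.

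**The concern.** With permuted blocks, hiding the list does not fully conceal the next allocation. Every block must end balanced, so the allocations already made carry information about the one to come. A person who knows them and also takes consent can, knowingly or not, adjust the timing of a visit or the warmth of an invitation to suit the arm that seems likely.

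Any imbalance produced this way enters before randomisation, so an intention-to-treat comparison does not remove it, and neither does blinded assessment. The primary model in the Data Analysis Plan adjusts only for baseline gait speed. The sensitivity covariates include age, frailty, comorbidity burden and length of stay, but not motivation or expected recovery. Patient activation is measured at baseline but is not a listed covariate. These traits plausibly matter for a walking test that depends on effort.

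**Working it through.** **Inputs from the documents.** Consenter roles, order of consent and randomisation, block sizes, and 3-4 patients recruited per month (Section D2.3). Access to allocations (Section D2.6). SD 0.29 m/s, target difference 0.18 m/s, 56 per group, two-sided alpha 0.05, clinically important difference 0.1 m/s (Sample Size Estimates).

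**Assumptions, because the documents are silent.** One unstratified 1:1 list. Block sizes 4 and 6 equally likely. A guesser who knows the two possible sizes but not their order. The steering difference delta and the share s, both defined in step 5.

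**1. The plan's own figure.** A two-sample t-test with difference 0.18, SD 0.29 and 90% power needs 55.5, so 56 per group and 112 in total. Power at 56 is 90.2%. Allowing for dropout, 112 / 0.75 = 149.3, or 150. The plan's sample size is confirmed and is not affected by this point. It also gives a scale for the bias: the standard error of the difference is 0.29 x sqrt(2/56) = 0.055 m/s.

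**2. Do the roles overlap?** Section D2.3 permits a research physical therapist to take home consent. Section D2.6 makes the research physical therapists trainers of both arms and readers of the data sheets, and its blinding paragraph unblinds those who train. No separate blinded group of research physical therapists is described, and no rule keeps unblinded staff out of recruitment.

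**3. Predictability with instant, complete knowledge.** If the size of the current block were known, exact enumeration gives 2.833/4 = 71% correct guesses for a block of 4 and 4.1/6 = 68% for a block of 6. Pooled, this is (2.833 + 4.1)/10 = 69%. The next arm would be certain for (1.333 + 1.5)/10 = 28% of assignments. With the order of block sizes unknown, simulation still gives 69% correct, but certainty falls to about 5.5%. The next arm is at least two-thirds likely for about 58% of assignments. The 69% is the same for lists of 150, 200 and 250.

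**4. Predictability with delayed knowledge.** Reading biweekly as every two weeks, 3-4 patients per month gives a lag of 3/2 = 1.5 to 4/2 = 2 patients. The rates below come from simulating the simple rule of guessing the arm that is behind.

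**5. Bias.** Suppose patients steered toward a guessed PHIT slot have a prognosis better by delta than those steered toward a guessed usual-care slot. Suppose also that a share s of participants is recruited by unblinded staff. With correct-guess rate p, the arms then differ by (2p - 1) x delta x s.

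| Lag (patients) | p | 2p - 1 | Bias in m/s, delta = 0.05, s = 25% | Bias in m/s, delta = 0.10, s = 25% |
|---|---|---|---|---|
| 0 | 0.692 | 0.38 | 0.005 | 0.010 |
| 1 | 0.594 | 0.19 | 0.002 | 0.005 |
| 2 | 0.556 | 0.11 | 0.001 | 0.003 |
| 3 | 0.520 | 0.04 | below 0.001 | 0.001 |

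Over lags of zero to two patients, the bias is (0.11 to 0.38) x delta x s, or about 0.001 to 0.010 m/s at s = 25%.

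**6. Consequence for the test.** The upper value, 0.010 m/s, is 0.010/0.055 = 0.18 standard errors. Two-sided type I error becomes P(Z > 1.78) + P(Z < -2.14) = 0.038 + 0.016, about 5.4% instead of 5%.

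**The case against.** The case for leaving the text alone has five parts.

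- **Identity.** The blinding paragraph unblinds only the research physical therapists who conduct training. Section C uses the same job label for staff who supervise outcome tests, so the label may cover others. This stands in part: the documents do not say that the home consenter is a trainer. But they make the research physical therapists the trainers, have them review data sheets from both arms, and do not separate the roles.
- **Existing safeguards.** The coordinator's custody of the list, central assignment and varying block sizes are real protections. Varying sizes make certainty rare. None of them returns the guess to 50% for someone who knows past allocations.
- **Control over recruitment.** A reader might infer that the therapist decides whether the next patient enters the trial. The documents do not support that. Physicians identify the hospital patients, the PRA takes hospital consent, and a research assistant may take home consent instead. What remains is influence over when and how a patient is approached.
- **Size.** A reader might combine instant knowledge, delta = 0.10 m/s and s = 100% to get 0.38 x 0.10 = 0.038 m/s, nearly 40% of the clinically important difference. That is not a fair reading. A share of 100% contradicts the PRA's role in hospital consent, delta has no source in the documents, and the formula assumes that every guess is acted on. The routine information channels are also delayed, although the blinding paragraph states no delay.
- **Unseen allocations.** Randomisation follows consent, and about 250 consent while 150 enrol, so (250 - 150)/250 = 40% may never generate a treatment data sheet. If those allocations are unseen at random (an assumption), simple rules based on recent history guess at most about 58% correctly with no lag, and 53-55% with a lag of one or two. If unblinded staff also learn these assignments, the gap closes. The documents do not say.

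The last two parts reduce the size. None removes the opportunity.

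**Conclusion.** The point holds as a cheap improvement. The plan lets people who know past allocations take consent on one home route and does not exclude them on the other, while randomisation follows in short blocks. That is an opportunity for selection bias on those routes. Nothing in the documents shows that selection took place, and it would be wrong to read the plan that way.

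The likely size is small: about 0.001-0.010 m/s at an assumed 25% share and delta of 0.05-0.10 m/s, which is at most a tenth of the clinically important difference. The true share is not given, only that it is below 100%. The figures rest on a single unstratified list, equally likely block sizes and a lag between zero and two patients. A longer lag or unseen allocations would make the bias smaller, and a larger share would make it larger in proportion.

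**What to change.** Three wording changes:

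1. In Section D2.3, remove the research physical therapist as an alternative home consenter, so that the research assistant already named takes consent from patients discharged beforehand.
2. In the community-referral text of the same section, put the same condition on the study team member who screens and consents.
3. In the blinding paragraph of Section D2.6, add that nobody with access to group assignments or intervention data sheets may screen, approach or consent patients.

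With no knowledge of past allocations, the guess rate on these routes returns to 50%. Sample size, randomisation method and analysis are unchanged, and no new staff are needed. The downside is slightly less flexible scheduling of home consent visits.
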